#### Exclusion criteria:

- a) Current suicidal ideation at study screening, defined as a response\_of  $\geq 2$  on item nine ("I have thoughts of killing myself but I would not carry them out") of the BDI-II
- b) If another household member is currently enrolled in the study
- c) Severe visual impairment, which may limit ability to utilize an app

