- b) Clinical deterioration: [name] and her research team will monitor participant PHQ-9 and BDI-II scores for possible clinical deterioration (i.e., increasing depressive symptoms and/or the development of suicidal ideation) throughout the course of the study as participants complete the PHQ-9 and BDI-II weekly. Clinical deterioration will be defined as an increase of 10 or more points on the BDI-II from the baseline BDI-II assessment or a response of "I would like to kill myself" or "I would kill myself if I had the chance" on the suicidal thoughts or wishes item of the BDI-II. Our team has developed alerts within REDCap reports that the investigative team checks daily to determine whether a participant completed a BDI-II assessment and evidenced evidences clinical deterioration. This system has now been implemented with success across multiple studies. In the event that a participant evidences clinical deterioration, [name] will contact the participant via phone and will provide referrals for local mental health resources for depression treatment. [name] will suggest that the participant seek treatment and then will follow-up with the participant via phone one week later. In the event that a participant reports suicidal ideation either during study screening or during subsequent assessments. [name] will 1) page the participant's attending primary care provider and 2) complete a risk assessment with the participant via phone. [name] will query the participant for details regarding the suicidal ideation, including a likelihood of harming oneself imminently and a plan for committing suicide. If the participant reports an imminent likelihood of harming him/herself or a plan for committing suicide, [name] will call emergency services and will remain on the phone with the participant until emergency services arrive. Contact information including home address will be collected during study screening and will be provided if necessary to emergency services personnel. [name] is a licensed clinical psychologist and has more than 10 years of experience conducting suicide risk assessments. In the event that a participant evidences clinical deterioration, the participant will be allowed to continue in the trial, but we will recruit an additional participant for data collection purposes.

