#### Adequacy of Protection Against Risks

#### Recruitment and Informed Consent

Study participants will be recruited from local primary care/family medicine clinics associated with MUSC's Primary Care Integrated Center of Clinical Excellence (ICCE). Study recruitment will occur proactively prior to a patient's scheduled primary care visit. We will utilize available EHR data to identify Primary Care ICCE patients with depressive symptoms. As part of routine clinical care, all primary care patients complete the Patient Health Questionnaire-2 (PHQ-2) to screen for depressive symptoms during each primary care visit. Information on depression is also available via the EHR within each patient's problem list and billing codes. Adult (age 18+) patients will be identified who have an upcoming visit scheduled within the next four weeks and have either: 1) a score of > 3 on their last PHQ-2 assessment (i.e., the optimal cut-point for identifying those who are symptomatic), 2) depression listed on their problem list, or 3) a depression-related billing code associated with their last visit. With the permission of their attending physician, these patients will be contacted by the study team via the patient EHR portal (MyChart) to invite them to participate in the research study. If participants do not respond to this initial invitation within 72-hours, we will contact them via phone, e-mail, and/or text-message (based on patient communication preferences within the EHR) to ensure they received the MyChart message. We currently implement this recruitment approach in an ongoing trial of an electronic visit for smoking cessation and our experience has been that it is feasible and efficient to generate a recruitment report via the EHR and that all physicians associated with the MUSC Primary Care ICCE have agreed to have their patients contacted for the purpose of our studies. If interested, participants will complete an eligibility screening via REDCap to determine preliminary study eligibility. After completing determination of preliminary eligibility, a member of the research team will schedule a phone call with the participant to determine final study eligibility (no suicidal ideation reported on the BDI-II). After determining final study eligibility, a member of the research team will complete informed consent with the participant. All participants will electronically/in writing sign informed consent forms that have been IRB-approved once the study is explained to them in full and they have stated that they understand what is being asked of them. Participants will be given the opportunity to ask questions about their participation throughout the course of the study. A copy of the informed consent will be kept centrally at our study office within

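### Suicidal ideation reported on the PHQ-9 has no described daily route to the clinician when the paired BDI-II does not meet the alert rule

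*Combined protocol and SAP*

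**What the plan says.** Section 13.0, item b) (Clinical deterioration), does four things in turn.

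- **Promise.** The study clinician and team "will monitor participant PHQ-9 and BDI-II scores for possible clinical deterioration (i.e., increasing depressive symptoms and/or the development of suicidal ideation". Both instruments are described as completed weekly.
- **Definition.** "Clinical deterioration will be defined as an increase of 10 or more points on the BDI-II from the baseline BDI-II assessment", or either of two responses on the BDI-II suicidality item: a stated wish to kill oneself, or "I would kill myself if I had the chance".
- **Daily detection.** The team has built "alerts within REDCap reports that the investigative team checks daily to determine whether a participant completed a BDI-II assessment" and whether it shows deterioration.
- **Response.** "In the event that a participant reports suicidal ideation either during study screening or during subsequent assessments", the clinician must page the attending primary care provider and "complete a risk assessment with the participant via phone". No instrument is named here, and the duty is not limited to the two alert responses.

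Elsewhere, item a) of the same section and the Protections Against Risk text describe symptom monitoring by the BDI-II alone. So does the adverse event definition in section 11.0. Under Trial Safety in section 12.0, the research assistant reports early signs of a serious psychiatric condition, with suicidality as the example, at the weekly meeting or sooner if urgent.

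**The concern.** The duty to respond is wider than the daily means of finding out. The plan names the PHQ-9 as an instrument watched for new suicidal ideation and requires action on ideation from any assessment. The one mechanism that someone is said to check every day looks only at the BDI-II.

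Section 7.0 says the research is conducted remotely, and participants enter with elevated depressive symptoms. The page and the phone call can begin only after someone has seen the answer. At stake is how promptly a clinician learns of an answer that the plan itself says must be acted on. This is a participant-safety matter.

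**Working it through.** No sample size, power or error rate is involved, so the check is a comparison of the relevant places.

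| Place | Instrument | Trigger | When looked at |
|---|---|---|---|
| 13.0 b), promise | PHQ-9 and BDI-II | worsening symptoms and/or new suicidal ideation | throughout the study, no interval given for the PHQ-9 |
| 13.0 b), alert | BDI-II | rise of 10 or more points, or either of two item responses | daily |
| 13.0 b), response | any assessment | suicidal ideation reported | once known |
| 13.0 a); Protections Against Risk | BDI-II | depressive symptoms; deterioration | no PHQ-9 step |
| 13.0 c) | none named | suicidal intent reported at any point | no detection step |
| 12.0, Trial Safety | none named | early signs, including suicidality | weekly meeting, or sooner if urgent |
| 12.0, Data and Safety Monitoring Plan Administration | outcomes database | missing data, odd distributions, outliers | monthly |

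**Counts.** The grid in section 4.0 places the PHQ-9 at Weeks 1 to 8 and Week 12: 8 + 1 = 9 follow-ups. The BDI-II is at the same nine, so 9 of 9 are paired. The described alert has two conditions on the BDI-II (the 10-point rise; either of the two responses) and 0 on the PHQ-9.

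**Cases at follow-up, given ideation on the PHQ-9.**

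1. The paired BDI-II has risen by 10 or more points, or carries one of the two responses. The daily alert fires and the clinician is reached.
2. The paired BDI-II has risen by less than 10 points and carries neither response. The alert as described does not fire, although the duty to page and call still applies. Detection is left to the general promise, the weekly-or-sooner report, or a monthly check aimed at data quality.

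Case 2 is the gap. The documents leave room for it. Item e) of section 13.0 lets participants decline any question, so if the survey form permits it, the BDI-II suicidality item could be blank while the PHQ-9 is answered.

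**A related inconsistency on the BDI-II itself.** The exclusion criteria define current suicidal ideation as a response of 2 or more on item nine and attach the wording "I have thoughts of killing myself but I would not carry them out". The Recruitment and Informed Consent text describes a call to "determine final study eligibility (no suicidal ideation reported on the BDI-II". The quoted wording is not one of the two alert responses. The documents do not print the item's score key, so it cannot be settled from them whether the numeric cut-off or the wording is the intended one.

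**The case against.** The strongest reply is that much is already covered. The team promises to monitor PHQ-9 scores throughout. The response step applies to any assessment. Suicidality is to be reported weekly or sooner if urgent. Every follow-up PHQ-9 has a BDI-II beside it, and section 13.0 reports ethics approval and successful prior use. All of this stands, and it narrows the point to discordant cases. It does not close the gap: urgency can be recognised only after someone reads the answer, and no step says who reads PHQ-9 answers or when. The reported success concerns the alert system described, which is BDI-II-based.

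A second reply is that the BDI-II is consistently the safety instrument, and the PHQ-9 mention in 13.0 b) is the outlier. The sentence can be read jointly, as two instruments for two signals, and the PHQ-9 items are not reproduced. That is a fair reading. Deleting the mention would tidy the sentence, but the duty to respond to ideation in any assessment would remain, without a daily look at the PHQ-9.

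Third, a reader might take the exclusion wording as proof of the PHQ-9 gap. It is not. A participant giving that response has reported it on the BDI-II, so this is a question of the BDI-II alert threshold, resting on ambiguous text. A PHQ-9 condition would catch that participant only if the PHQ-9 agreed. It is therefore kept as a separate item.

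Finally, the text describes an alert; the built system may do more. If so, writing it down costs little.

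**Conclusion.** The point holds in limited form: as written, daily detection covers less than the plan's own duty to respond. The uncovered cases are those with ideation on the PHQ-9 and a paired BDI-II that does not meet the deterioration rule. Their number, and any resulting delay, cannot be derived from the documents.

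Stronger readings should be resisted.

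- A reader might infer that PHQ-9 ideation goes unmonitored or unanswered. The general promise, the instrument-neutral response and the weekly-or-sooner report contradict that.
- A reader might multiply 695 participants by 9 follow-ups (695 × 9 = 6,255) and call all of them exposed. The pairing with the BDI-II means that only discordant ones are.
- A reader might infer a fixed delay of a week from the weekly meeting. The provision for earlier reporting rules that out.
- A reader might infer that 13.0 b) lets PHQ-9 totals drive the deterioration definition. It does not; the definition is explicitly on the BDI-II, and no rewording on that ground is needed.

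The conclusion assumes that the PHQ-9 can elicit suicidal ideation, taken from 13.0 b) itself, and that the alert works as described. Confidence is medium. This is a cheap improvement with no bearing on efficacy inference, sample size or alpha.

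**What to change.** Add to the existing daily REDCap alert report a condition for suicidal ideation reported on the PHQ-9. The study clinician should set the triggering response level, and the protocol should state it. Route a positive flag to same-day clinician review and the risk assessment in section 13.0, item b).

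Separately, reconcile the numeric cut-off and the quoted wording in the exclusion criteria with the two BDI-II responses that fire the alert. If the quoted response counts as suicidal ideation, flag it for clinician review as well.

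Leave the 10-point BDI-II rule and the adverse event definition in section 11.0 unchanged.

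The cost is one added condition in a report already checked daily, a further BDI-II flag if the reconciliation calls for it, and a short protocol amendment. No new assessment is needed. The downside is more alerts and phone calls, including repeats for participants with stable low-level ideation; the documents give no figure for that workload.

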#### Adequacy of Protection Against Risks

#### Recruitment and Informed Consent

Study participants will be recruited from local primary care/family medicine clinics associated with MUSC's Primary Care Integrated Center of Clinical Excellence (ICCE). Study recruitment will occur proactively prior to a patient's scheduled primary care visit. We will utilize available EHR data to identify Primary Care ICCE patients with depressive symptoms. As part of routine clinical care, all primary care patients complete the Patient Health Questionnaire-2 (PHQ-2) to screen for depressive symptoms during each primary care visit. Information on depression is also available via the EHR within each patient's problem list and billing codes. Adult (age 18+) patients will be identified who have an upcoming visit scheduled within the next four weeks and have either: 1) a score of > 3 on their last PHQ-2 assessment (i.e., the optimal cut-point for identifying those who are symptomatic), 2) depression listed on their problem list, or 3) a depression-related billing code associated with their last visit. With the permission of their attending physician, these patients will be contacted by the study team via the patient EHR portal (MyChart) to invite them to participate in the research study. If participants do not respond to this initial invitation within 72-hours, we will contact them via phone, e-mail, and/or text-message (based on patient communication preferences within the EHR) to ensure they received the MyChart message. We currently implement this recruitment approach in an ongoing trial of an electronic visit for smoking cessation and our experience has been that it is feasible and efficient to generate a recruitment report via the EHR and that all physicians associated with the MUSC Primary Care ICCE have agreed to have their patients contacted for the purpose of our studies. If interested, participants will complete an eligibility screening via REDCap to determine preliminary study eligibility. After completing determination of preliminary eligibility, a member of the research team will schedule a phone call with the participant to determine final study eligibility (no suicidal ideation reported on the BDI-II). After determining final study eligibility, a member of the research team will complete informed consent with the participant. All participants will electronically/in writing sign informed consent forms that have been IRB-approved once the study is explained to them in full and they have stated that they understand what is being asked of them. Participants will be given the opportunity to ask questions about their participation throughout the course of the study. A copy of the informed consent will be kept centrally at our study office within

locked filing cabinets and a copy will also be given to each study participant. Participants will be given a study phone number and e-mail address to contact for questions.

## Protections Against Risk

All screening information will be kept in a password protected REDCap database. Only key study personnel will have access to the database. If an individual is not eligible to participate, his/her screener will include his/her first name and last initial and the reason for disqualification. Eligible participants' full name, telephone number and e-mail address will be recorded in the database. This is the only place where participants' names and subject identification numbers appear together. Eligible participants will be assigned a subject number, will complete informed consent (see procedures above), will be randomized (Aim 2), will complete baseline assessments, and subsequently will receive their randomized intervention (or will complete usability testing).

Upon completing eligibility screening, if study eligible, individuals will be provided with a verbal overview of the study, asked to review a consent form, and asked to provide informed consent. Participants will be informed of limitations of confidentiality (i.e., abuse or neglect, intention to harm self or someone else) both verbally and in writing during the informed consent process. The consent form will include the participant's name, but not his/her subject number. Consent forms will be provided in English. As utilization of Moodivate requires that participants are able to read, participants unable to read the consent form on their own will not be included.

Regarding questionnaire data, data will be obtained for research purposes only. All data will be collected, stored, and managed via REDCap, which is a secure, web-based application designed exclusively to support data capture for research studies. REDCap includes real time validation rules with automated data type and range checks at the time of entry. The underlying database is hosted in a secure data center at MUSC and includes redundancy, failover capability, backups and extensive security checks. The system has several layers of protection including user/group account management, "Data Access Groups" which allow data to be entered by multiple groups in one database with segmented user rights for entered data, audit trails for all changes, queries and reports, and Secure Sockets Layer (SSL) encryption. Name and relevant contact information will be obtained to provide compensation and every effort will be made to maintain subject confidentiality, in accordance with HIPAA. All data will be identified only by code numbers (participant IDs). Participant IDs will be linked to participants' names in a password-protected file that is accessible only to the PI and trained research staff.

Regarding user privacy while using Moodivate, users will create a username and password in order to login to their account without storing their true identity. Users will be instructed not to use identifiable information in their username (e.g., name, birthdate, etc) to protect identity. In Moodivate, we will store a one-way hashed version of the patient's email address to support password reset and unique identification, but that identification will not be traceable back to the user's true identity. We will not store any personally identifiable information (e.g., first name, last name, email address, phone number) of users in our app database. We will use a HIPAA-compliant server protected by industry-standard safeguards to prevent unauthorized access. Since we are not associating patient health information with personally identifiable information there would not be a risk of unauthorized release of patient medical data in the event of a security breach. User personal information will be contained behind secured networks and will only be accessible by the investigators, who will have special access rights to such systems. In addition, all sensitive information users supply will be encrypted via Secure Socket Layer (SSL) technology. We will not sell, trade, or otherwise transfer personally identifiable information to outside parties. Our privacy policy will be available within the app for users to view at any time. This plan is consistent with that used by our partnering app development company, MountainPass Technology LLC, in several other previous products with similar protection requirements.

Protection against risk resulting from depressive symptoms includes the following: Regarding suicidal ideation and broader mental health concerns, [name], a licensed clinical psychologist, will take appropriate action as outlined by the MUSC IRB, NIH, and the State of South Carolina, which may include paging the participant's referring physician, contacting the authorities and/or pursuing involuntary commitment at a mental health facility. If participants present no imminent danger but also need more extensive treatment of mental health concerns, they will be given appropriate referrals. As noted above, BDI-II data will be monitored over time in order to detect any possible clinical deterioration. BDI-II data will be monitored using only the participants' subject numbers. Should a participant evidence clinical deterioration, [name] will then use the participant database in order to obtain contact information for the participant based on their subject number. We will also form a Data Safety and Monitoring Board (DSMB). If the percent of serious or severe AEs related to clinical deterioration appears to be greater than 5% the DSMB will be notified to make a decision on early termination of the study.

# 14.0 Potential Benefits to Subjects or Others

All participants in this trial will receive at minimum treatment as usual via MUSC's Primary Care ICCE clinics. We will not augment treatment as usual as provided by these clinics. The majority of participants will also receive a mobile app developed to improve depressive symptoms. The major benefit to society will be whether Moodivate and/or Moodivate + EHR integration improves depression treatment outcomes relative to TAU. Potential issues of clinical deterioration, confidentiality, data security, and frustration are a high priority and will be closely monitored throughout the study. Consequently, the risk to benefit ratio in the proposed study appears to be acceptable.

# 15.0 Sharing of Results with Subjects

Study outcomes will not be shared with subjects.

